1.1 Rationale

A first-in-human study has been completed to evaluate the safety, tolerability, and pharmacokinetics (PK) of IV administered OP-101 in normal healthy humans. This study indicated that treatment with a single IV dose of OP-101 at 20 and 40 mg/kg was generally well tolerated in healthy subjects based on an assessment of clinical and laboratory adverse events. The half-life of OP-101 in this study (5.5 hr) demonstrated the need for development of a more convenient dosing route (e.g. subcutaneous). This study is being conducted to enable selection of the starting dose and regimen in a planned Phase 1/2/3 study in patients with ccALD. Currently, ccALD patients with progressive disease not treatable with HSCT have no therapeutic options, and reactive microglia are a recognized cause of the neuroinflammation associated with progression in ccALD. OP-101 has been demonstrated to selectively target reactive microglia and astrocytes in animal models of neuroinflammation, and has also been shown *ex vivo* to be effective in normalizing activated macrophages cells derived from ccALD patients. By targeting the reactive microglia, OP-101 has the potential to stop or slow neurodegeneration in ccALD patients through antioxidant and anti-inflammatory mechanisms and may provide clinical benefit to ccALD patients not eligible for HSCT. Reversing the neuroinflammation driving the white matter injury in ccALD patients could stabilize the disease course and preserve neurological, developmental, and cognitive function.

The safety and PK data collected in this subcutaneous dosing study will permit identification of the starting dose and regimen for the Phase 1/2/3 study in ccALD and support further clinical development of OP-101.

1.2 Risk/Benefit

This study is a follow up to the completed Phase 1 single ascending IV dosing study in healthy volunteers. In the completed Phase 1 study, treatment with a single IV dose of OP-101 at 20 and 40 mg/kg was generally well tolerated in healthy subjects based on an assessment of clinical and laboratory adverse events. There were no clinically meaningful changes from baseline in laboratory parameters except changes in the urinalysis parameters of proteinuria and the presence of granular urinary casts. Transient elevations in KIM-1 and NGAL were observed, and subjects who experienced an increase in KIM-1 or NGAL at Day 15 underwent additional follow-up, at the recommendation of the SRC. The additional measurements in either KIM-1 or NGAL were

conducted as a precautionary measure and the values subsequently returned to baseline. There were no clinically meaningful changes in vital signs or ECGs. OP-101 has also been tested in nonclinical studies with no adverse clinical changes observed across multiple species and models. The anticipated risks associated with OP-101 may be categorized as potentially related to the PAMAM dendrimer and/or NAC. In vitro studies have demonstrated that the dendrimer is not systemically metabolized in human hepatocytes or human plasma and is rapidly cleared by the kidney. Good Laboratory Practice toxicity studies with repeat dosing of OP-101 in juvenile and adult rats have shown partial dose-dependent changes of proximal tubular cells characterized by mild intracellular basophilia and mild single-cell necrosis, but no associated clinical adverse events, mortality, or change in electrolytes. Toxicology studies in rats with single-doses of OP-101 have demonstrated resolution of the single-cell necrosis by 2 weeks postdosing and no adverse clinical observations or changes in urinalysis parameters. In summary, the renal clearance of OP-101 and the effects on proximal tubular cells in nonclinical studies indicate that renal function should be carefully assessed in human studies.

The active metabolite of OP-101, NAC, is an approved product and marketed under Acetadote. NAC is only released from OP-101 under intracellular GSH levels, and lower levels of GSH in plasma are insufficient to release NAC systemically. Regardless, the total level of NAC, if completely released from the highest possible human OP-101 dose, is well below the total systemic NAC typically administered for acetaminophen toxicity. Thus, the risks associated with Acetadote are relevant but unlikely to manifest given the projected low systemic exposure to NAC, even if fully released upon administration. For completeness, the major adverse events associated with IV NAC administration have been categorized as anaphylactoid reactions, with most either mild or moderate in degree. The most common adverse effects associated with NAC infusion were minor anaphylactoid reactions, including rash, urticarial, hypotension, and wheezing or shortness of breath. Literature reports indicate that adverse reactions consistent with hypersensitivity have been easily treated with antihistamines, epinephrine, and/or slowing of the drug infusion. Other reported adverse events related to IV NAC administration include tachycardia, nausea, and emesis. The frequency of adverse events has been reported to be between 0.2% and 20.8% and most commonly occur during the initial IV infusion of Acetadote (Acetadote Prescribing Information, Cumberland Pharmaceuticals Inc.).

In summary, clinical risks associated with the proposed subcutaneous (SC) doses of OP-101 are considered low based on the lack of clinical adverse events observed at 3-5 fold higher doses administered IV in healthy volunteers. In addition, the human safety profile established for NAC, which is the active moiety in OP-101, further predicts a favorable safety profile and low risk with human investigation.

There is no expected benefit of IV OP-101 administration for normal healthy subjects. Although safety and efficacy of OP-101 have not yet been evaluated in clinical studies, the collective efficacy observed in nonclinical studies indicate the potential to reverse neuroinflammation by targeting the reactive microglia in patients with ccALD. Because of the central role of neuroinflammation in driving disease progression in ccALD, the potential benefit in the intended patient population could include stabilization of white matter injury, and therefore the preservation of motor, cognitive, and developmental functions similar to the treatment effect after successful HSCT.

2 STUDY OBJECTIVES

2.1 Primary Objective

The primary objective is to evaluate the safety and tolerability of OP-101 after single SC doses in healthy subjects.

2.2 Secondary Objective

The secondary objective is to determine the pharmacokinetic (PK) profile of OP-101 after single SC doses in healthy subjects.

3 STUDY DESCRIPTION

3.1 Summary of Study Design

This is a Phase 1, open-label, single-ascending dose study to evaluate the safety, tolerability, and PK of OP-101 after SC administration in up to 8 healthy subjects at 1 site in Australia.

This study will consist of a 21-day Screening Period, a 2-day Treatment Period, and Follow-up Visits on Days 8 and 15. Subjects will sign an informed consent form (ICF) before any study procedures are performed and must meet all of the inclusion and none of the exclusion criteria to participate in the study. Eligible subjects will be admitted to the investigational site on Day -1, dosed on Day 1, and discharged on Day 3.

[figure not shown]
Figure 1 presents the cohort dosing schematic. There will be 2 separate and sequential SC cohorts (4 mg/kg and 8 mg/kg) with 4 subjects in each cohort who complete Day 15. Cohort 1 will enroll 4 subjects administered a single SC dose of 4 mg/kg. Dose escalation from Cohort 1 (4 mg/kg) to Cohort 2 (8 mg/kg) will be determined by the safety review committee (SRC), consisting of the Medical Monitor, the Principal Investigator (or delegate), and Sponsor representative after review of safety, tolerability, and any available PK data through Day 8 of Cohort 1. Cohort 2 will enroll 4 subjects administered a single SC dose of 8 mg/kg.

During the Treatment Period, plasma and urine samples will be collected for PK analysis. Plasma PK samples will be collected predose, at 30 minutes and at 1, 2, 4, 6, 8, 10, 12, 16, 24, and 30-36 hours after dosing, as well as on Day 3 (~48 hr). Blood samples for PK analysis can be obtained within ± 5 minutes of the scheduled sampling time for sample times ≤ 1 hour, within ± 10 minutes of the scheduled sampling time for sample times ≤ 12 hours, and within ± 2 hours of the scheduled sampling times for sample times > 12 hours.

Urine PK samples will be collected predose (spot sample) and between 0 to 4, 4 to 8, 8 to 12, 12 to 18, 18 to 24, and 24 to 48 hours.

Safety assessments will include adverse event monitoring, clinical laboratory tests (hematology, chemistry, and urinalysis), physical examinations, and vital signs (pulse rate, blood pressure [BP], respiration rate, and temperature). Coagulation testing will be performed at screening. Pregnancy testing will be performed at screening and Day -1.

Figure 1. OP-101 Single-Ascending Subcutaneous Dose Schedule – Day 1

1. Cohort enrollment will be separate and sequential with 4 subjects in each cohort who complete Day 15.
2. Cohort 1 will enroll 4 subjects administered a single SC dose of 4 mg/kg OP-101. Dose escalation to Cohort 2 (8 mg/kg) will be determined by the SRC after review of safety, tolerability and any available PK data through Day 8 of Cohort 1. Cohort 2 will enroll 4 subjects administered a single SC dose of 8 mg/kg.

PK = pharmacokinetic(s); SRC = safety review committee.

3.2 Study Stopping Rules

This study will stop and no further dosing and/or dose escalation will occur until safety information can be reviewed in the event that:

- 1 subject within a dose cohort has a drug-related Grade 3 adverse event or serious adverse event (SAE), or
- ≥ 2 subjects within the same dose cohort have a drug-related Grade 2 adverse event.

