5 STUDY TREATMENTS

5.1 Treatment Groups

There will be 2 separate and sequential SC cohorts with 4 subjects in each cohort. The population will include healthy men and women aged 18 to 65 years, inclusive.

Dose escalation from Cohort 1 to Cohort 2 will be determined by the SRC, consisting of the Medical Monitor, the Principal Investigator (or delegate), and Sponsor representative after review of safety, tolerability, and any available PK data through Day 8 of Cohort 1.

Dosing with OP-101 is planned for the cohorts as follows:

- Cohort 1: Single SC dose of 4 mg/kg, and
- Cohort 2: Single SC dose of 8 mg/kg.

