Clinically significant abnormal laboratory or other examination findings that are detected during the study or are present at screening and significantly worsen during the study should be reported as adverse events. The Investigator will exercise his or her medical and scientific judgment in deciding whether an abnormal laboratory finding or other abnormal assessment is clinically significant. Clinically significant abnormal laboratory values occurring during the clinical study will be followed until repeat tests return to normal, stabilize, or are no longer clinically significant. Any abnormal test that is determined to be an error does not require reporting as an adverse event.

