8.1.3 Assessment of Adverse Events by the Investigator

The Investigator will assess the severity (intensity) of each adverse event as mild, moderate, or severe, and will also categorize each adverse event as to its potential relationship to study drug using the categories of yes or no.

The severity of all adverse events should be graded according to the Common Terminology Criteria for Adverse Events (CTCAE) Version 5.0. These criteria can be found at <http://ctep.cancer.gov/reporting/ctc.html>. For those adverse events not listed in the CTCAE, the following grading system should be used:

- Mild (CTCAE Grade 1): Transient symptoms, awareness of sign/symptom, but easily tolerated and no interference with subject's daily activities.
- Moderate (CTCAE Grade 2): Marked signs/symptoms that interfere with subject's usual activities, but still acceptable.
- Severe (CTCAE Grade 3): Incapacitating signs/symptoms which cause considerable interference with the subject's daily activities, unacceptable.
- Life-threatening (CTCAE Grade 4): Life threatening or disabling adverse event.
- Death (CTCAE Grade 5): Death-related adverse event.

Causality Assessment

The relationship of an adverse event to the administration of the study drug is to be assessed according to the following definitions:

No (unrelated, not related, no relation) – The time course between the administration of study drug and the occurrence or worsening of the adverse event rules out a causal relationship and another cause (concomitant drugs, therapies, complications, etc.) is suspected.

Yes (related) – The time course between the administration of study drug and the occurrence or worsening of the adverse event is consistent with a causal relationship and no other cause (concomitant drugs, therapies, complications, etc.) can be identified.

The definition implies a reasonable possibility of a causal relationship between the event and the study drug. This means that there are facts (evidence) or arguments to suggest a causal relationship.

The following factors should also be considered:

- The temporal sequence from study drug administration-
 - The event should occur after the study drug is given. The length of time from study drug exposure to event should be evaluated in the clinical context of the event.
- Underlying, concomitant, intercurrent diseases-

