8.2 Serious Adverse Events

An adverse event or adverse reaction is considered serious if, in the view of either the Investigator or Sponsor, it results in any of the following outcomes:

- Death,
- A life-threatening adverse event,
 - NOTE: An adverse event or adverse reaction is considered “life-threatening” if, in view of either the Investigator or Sponsor, its occurrence places the subject at immediate risk of death. It does not include an event that, had it occurred in a more severe form, might have caused death.
- Requires hospitalization or prolongation of existing hospitalizations,
 - NOTE: Any hospital admission with at least 1 overnight stay will be considered an inpatient hospitalization. An emergency room visit without hospital admission will not be recorded as a SAE under this criterion, nor will hospitalization for a procedure scheduled or planned before signing of informed consent. However, unexpected complications and/or prolongation of hospitalization that occur during elective surgery should be recorded as adverse events and assessed for seriousness. Admission to the hospital for social or situational reasons (ie, no place to stay, live too far away to come for hospital visits) will not be considered inpatient hospitalizations.
- A persistent or significant disability/incapacity or substantial disruption of the ability to conduct normal life functions,
- A congenital anomaly/birth defect, or
- An important medical event.
 - NOTE: Important medical events that may not result in death, be life-threatening, or require hospitalization may be considered an SAE when, based upon appropriate medical judgment, they may jeopardize the subject and may require medical or surgical intervention to prevent one of the outcomes listed above. Examples of such medical events include allergic bronchospasm requiring intensive treatment in an emergency room or at home, blood dyscrasias or convulsions that do not result in inpatient hospitalizations, or the development of drug dependency.

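### The stopping rule names exact grades without "or higher", so a non-serious drug-related Grade 4 event triggers no pause although a Grade 3 event does

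*Protocol*

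**What the plan says.** Protocol Section 3.2 sets two triggers for stopping until safety information can be reviewed.

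- First: "1 subject within a dose cohort has a drug-related Grade 3 adverse event or serious adverse event (SAE), or"
- Second: "≥ 2 subjects within the same dose cohort have a drug-related Grade 2 adverse event"

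In the second trigger the ≥ sign applies to the number of subjects, not to the grade. No other section of the protocol extends either grade upward, and the SAP does not restate the rule.

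Section 8.1.3 grades all events on CTCAE. Its fallback wording for events not listed there places this level above Grade 3: "Life-threatening (CTCAE Grade 4): Life threatening or disabling adverse event".

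Section 8.2 defines seriousness separately. An event counts as life-threatening if "its occurrence places the subject at immediate risk of death", with the qualification: "It does not include an event that, had it occurred in a more severe form, might have caused death". Important medical events "may be considered an SAE when, based upon appropriate medical judgment, they may jeopardize the subject", which leaves that route to judgement.

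Section 8.1 directs that these be reported as adverse events: "Clinically significant abnormal laboratory or other examination findings that are detected during the study". The grade-based triggers therefore reach laboratory findings.

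Section 5.1 gives the other safeguard: "Dose escalation from Cohort 1 to Cohort 2 will be determined by the SRC", after review of Cohort 1 data through Day 8.

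**The concern.** A stopping rule should never react to a milder event and ignore a worse one. This rule does so for any drug-related Grade 4 event that neither the investigator nor the sponsor classes as serious. Such an event is not Grade 3, not an SAE and not Grade 2, so it meets neither trigger.

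The case is relevant here because the expected toxicity is largely detected by laboratory tests. Section 1.2 reports proteinuria, granular casts and transient KIM-1 and NGAL elevations in the intravenous study, and proximal tubular changes in rats. A laboratory finding can be graded without posing an immediate risk of death. Section 4.3 itself lists severe laboratory abnormalities separately from SAEs as reasons for withdrawal.

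Section 3.2 is the only mandatory pause described within a cohort. The people exposed by the gap are mainly healthy volunteers in the same cohort who have not yet been dosed. Escalation to 8 mg/kg has its own committee decision, but no later escalation review is described for Cohort 2.

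**Working it through.** The documents give no operating characteristic for the rule, so there is no stated figure to reproduce. The check applies the rule as written and an or-higher version to the same cases.

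**Inputs.** Four subjects per cohort (Section 5.1); the triggers in Section 3.2; Grades 1 to 5 (Section 8.1.3). Assumption: each subject has at most one drug-related, non-serious event, so each subject's state is none or Grade 1, 2, 3 or 4. Grade 5 is excluded because death is always an SAE.

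**Individual cases, all events non-serious**

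| Events in a cohort of 4 | As written | Or higher |
|---|---|---|
| One Grade 3 | stop | stop |
| One Grade 4 | no stop | stop |
| Two Grade 2 | stop | stop |
| One Grade 2 and one Grade 4 | no stop | stop |
| Two Grade 4 | no stop | stop |
| Four Grade 4 | no stop | stop |

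**Counting patterns.** With k states per subject there are C(k + 3, 4) unordered patterns of 4 subjects.

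- All patterns, k = 5: C(8, 4) = 70.
- Patterns with at least one Grade 4: 70 − C(7, 4) = 70 − 35 = 35.
- Rule as written: 70 − 35 = 35 patterns contain a Grade 3. Without a Grade 3, those with two, three or four Grade 2 events number 6 + 3 + 1 = 10. Total 45.
- Or-higher rule: 70 − C(6, 4) = 70 − 15 = 55 patterns contain a Grade 3 or 4. Without either, those with at least two Grade 2 events number 3 + 2 + 1 = 6. Total 61.
- Missed: 61 − 45 = 16.
- Direct check: a missed pattern has a Grade 4, no Grade 3 and at most one Grade 2. With no Grade 2 there are 15 − 5 = 10. With one Grade 2 there are 10 − 4 = 6. Total 16.

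**Which edit matters.** With the first trigger amended alone, all 55 patterns containing a Grade 3 or 4 stop. The remaining patterns go no higher than Grade 2, where the second trigger already works, so 0 are missed. With the second trigger amended alone, a single Grade 4 whose three companions have nothing or Grade 1 is still missed, which is 4 patterns.

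**Including serious events.** Give each subject ten states (none, non-serious Grades 1 to 4, serious Grades 1 to 5) and count ordered cohorts, 10⁴ = 10,000 in all. The two versions differ when nobody has a serious event or a Grade 3, at least one subject has a Grade 4, and at most one has a Grade 2: (3⁴ − 2⁴) + 4 × (3³ − 2³) = 65 + 76 = 141. Every one contains a non-serious Grade 4 event. This is the same gap on a wider list of states.

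None of these counts is a probability. The frequency of non-serious Grade 4 events cannot be derived from the documents.

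**The case against.** The strongest reply is that every reader will take Grade 3 as a floor. The first trigger also says 1 subject without a ≥ sign, and nobody takes that to exclude two subjects; read that strictly, the rule would stop in 31 of the 70 patterns. The comparison is fair but not exact. The first affected subject triggers the stop, so a count of 1 works as a floor in practice. An event's grade does not pass through Grade 3 in that way. The sponsor's intention is probably as the reply says, but a mandatory rule should not depend on inferring it.

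Second, the printed Grade 4 wording, life-threatening or disabling, largely overlaps the SAE criteria, and either the investigator or the sponsor may call an event serious. This stands as a limit on the gap. It does not close it: that wording covers only events not listed in CTCAE, the disability criterion in Section 8.2 requires persistence, significance or substantial disruption, and nothing makes every Grade 4 event serious. The documents do not reproduce the CTCAE laboratory thresholds, so no particular analyte is claimed.

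Third, the consequences are small. Each subject receives one dose, and the first scheduled post-dose safety laboratory sample is at 24 hours (Section 6.3.2), so a pause for a laboratory finding would protect only subjects dosed after that result. Committee review precedes escalation, and a voluntary pause is always possible. All of this stands and keeps the point minor.

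Finally, the drawing in Figure 1 was not available for this check. Its footnotes and the protocol text state no dosing stagger within a cohort, but the drawing itself could not be checked.

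**Conclusion.** The point holds as a minor drafting defect in a safety rule. Followed literally, Section 3.2 stops dosing for one non-serious drug-related Grade 3 event and not for a Grade 4 one. Under the stated assumption, the wording misses 16 of the 35 patterns that contain a Grade 4 event, and misses none without one. After the first such event, anywhere from 0 to 3 of the cohort's 4 subjects could still be undosed, since the text fixes no stagger.

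The conclusion rests on the literal wording and on Grade 4 events that nobody classes as serious. It makes no claim about how often these occur. No analysis population, summary or estimate is affected.

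**What to change.** In Section 3.2, insert *or higher* after Grade 3 in the first trigger and after Grade 2 in the second, and write the first subject count as ≥ 1 to match the second. The first insertion alone closes all 16 missed patterns. The second keeps the two triggers consistent and is not sufficient by itself.

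The cost is two short wording changes, plus possibly an extra temporary pause until the safety information has been reviewed.

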3.3 Study Indication

OP-101 is being developed for the treatment of children with ccALD who are not eligible for HSCT.

4 SELECTION AND WITHDRAWAL OF SUBJECTS

4.1 Inclusion Criteria

Subjects who meet all of the following criteria will be eligible to participate in the study:

1. Is a healthy man or woman age 18 to 65 years, inclusive, at the Screening Visit;
2. Has the ability to understand and sign the written ICF and local medical privacy authorization forms, which must be obtained prior to any study related procedures being completed;
3. Body mass index (BMI) between 18 and 32 kg/m², inclusive;
4. Is in general good health, based upon the results of a medical history assessment, physical examination, vital signs, and laboratory profile, as judged by the Investigator;
5. Female subjects of non-childbearing potential must be either surgically sterile (hysterectomy, bilateral tubal ligation, salpingectomy, and/or bilateral oophorectomy at least 26 weeks before the Screening Visit) or postmenopausal, defined as spontaneous amenorrhea for at least 2 years, with follicle-stimulating hormone (FSH) in the postmenopausal range at screening, based on the central laboratory's ranges;
6. Female subjects of childbearing potential (ie, ovulating, premenopausal, and not surgically sterile) and all male subjects must use a medically accepted contraceptive regimen (including hormonal contraceptives) during their participation in the study and for 30 days after the last administration of study drug. Medically accepted contraceptive methods are defined as those with 90% or greater efficacy;
7. Acceptable methods of contraception for male subjects enrolled in the study include the following:
 - Condoms or surgical sterilization of subject at least 26 weeks before the Screening Visit (vasectomy);

Acceptable methods of contraception for female subjects enrolled in the study include the following:

- Surgical sterilization of subject at least 26 weeks before the Screening Visit (includes hysterectomy or bilateral tubal ligation, oophorectomy, or salpingectomy);
 - Intrauterine device for at least 12 weeks before the Screening Visit;
 - Hormonal contraception (oral, implant, injection, ring, or patch) for at least 12 weeks before the Screening Visit; or
 - Diaphragm;
8. If male, subjects must agree to abstain from sperm donation through 90 days after administration of the last dose of study drug;
 9. Female subjects may not be pregnant, lactating, or breastfeeding;
 10. Female subjects of childbearing potential must have negative result for pregnancy test at screening and Check-in;

11. Subjects must have a negative test result for hepatitis B surface antigen (HBsAg), hepatitis C virus antibody (HCVab), and human immunodeficiency virus (HIV) antibody at screening;
12. Subjects must have an estimated glomerular filtration rate (eGFR) of ≥ 90 mL/min/1.73m² at screening;
13. Subjects must have a negative urine test for drugs of abuse (opiates, benzodiazepines, amphetamines, cannabinoids, cocaine, barbiturates, and phencyclidine), cotinine, and breath alcohol test at screening and Check-in; and
14. Subjects must be willing and able to abide by all study requirements and restrictions.

